**Statistical analysis, sample size calculations and timeline:** The primary measure for PA/A is ADP-induced AUC assessed by platelet aggregometry. ADP-induced AUC will be compared between the LLH and no LLH groups with an unpaired Student's t test. The null hypothesis is that there will be no difference in the PA/A between groups. A prior in-vitro study suggested that LLH increases PA/A by at least 30% as measured by aggregometry from  $20\pm 5$  to  $26\pm 4$  AU [12]. If this is the true population effect of LLH on PA/A in patients with CF pumps, with a minimum of 15 patients in each group per device we would achieve **90% power** to detect a significant difference in means with a two-sided alpha of 0.05. Since there will be fewer patients with LLH, we will recruit for both groups until we have enrolled 15 patients in the LLH group for each device. As device specific comparisons will be made, for durable CF pumps we estimate that we will have to screen 80 HM2 and 115 HM3 patients. We estimate that 35% of these patients will be excluded due to being on sildenafil, nitrates, active infection or withholding consent. This will leave 50 HM2 and 75 HM3 patients available for analysis. From historical data [30], we expect that approximately 30% of HM2 (n=15) patients and 20% of HM3 (n=15) will have LLH and the remainder will be in the no LLH group (35 HM2, 60 HM3). For acute CF pump support, we estimate that 90 VA ECMO and 90 Impella patients will need to be screened and after 50% exclusion, 45 VA ECMO and 45 Impella will be enrolled and available for analysis. Based on our preliminary data (**Figure 3C**) for VA ECMO and prior reports in Impella [31], we expect that at least 35% of patients for each acute CF pump (n=15 per device) will have LLH and the remainder will be in the no LLH group (n=30). At our institution there are 5 durable CF pumps implants (3 HM3 and HM2) and 6 acute support CF pumps (3 VA ECMO and 3 Impella) implanted every month. In addition, there are currently 125 stable outpatients with durable CF pumps (95 HM2 and 30 HM3) available for screening. Therefore, we estimate it would take 32 months to enroll and analyze the calculated number of patients for all devices (see timeline). For each device specific comparison, we will examine the confounding effects of age, sex, body mass index, race/ethnicity (such variables are known to effect

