thrombosis during CF MCS) by comparing them between LLH and no LLH groups. If significant differences are found then adjusted multivariable models will be used to assess the independent association of LLH and PA/A. We will also assess if there are device differences by conducting a 1-way ANOVA test of the difference PA/A between LLH and no LLH amongst all 4 device groups and post-hoc comparisons if any significant difference is observed. Results from devices that do not show heterogeneity will be pooled to assess the association across device type. Similar to the device specific analysis noted above, confounders will also be examined, and if appropriate, adjusted for in this pooled sample. Lastly, we will compare for each device and in any pooled analysis, the association of LLH with potential mediators of PA/A including p-selectin, activated GP IIb/IIIa receptor, cGMP, vWF activity, UL/HMW multimers, ADAMTS 13 activity by unpaired Student's t tests.

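### Aim 1 lets a non-significant heterogeneity test decide whether devices are pooled, and at the planned sizes that test usually misses a halving of the LLH effect in one or both acute devices

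*Combined protocol and SAP*

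**What the plan says.** The relevant text is in the combined protocol and SAP, Aim 1, *Statistical analysis, sample size calculations and timeline*.

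- **Per-device analysis.** "ADP-induced AUC will be compared between the LLH and no LLH groups with an unpaired Student's t test". The size is set within a device: the plan claims 90% power at a two-sided 0.05 level "with a minimum of 15 patients in each group per device we would achieve" it.
- **Planned numbers.** For durable pumps, the plan expects that "approximately 30% of HM2 (n=15) patients and 20% of HM3 (n=15) will have LLH". Patients without LLH number 35 on HM2 and 60 on HM3. For each acute pump, ("n=15 per device) will have LLH and the remainder will be in the no LLH group (n=30").
- **Heterogeneity step.** Device differences are assessed by "conducting a 1-way ANOVA test of the difference PA/A between LLH and no LLH amongst all 4 device groups", with post-hoc comparisons if the result is significant.
- **Pooling rule.** "Results from devices that do not show heterogeneity will be pooled to assess the association across device type".
- **Mediators.** The mediators are compared by LLH status within each device and also in any pooled sample, by unpaired t tests.

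The plan gives no significance level, equivalence margin, confidence-interval criterion or power for the heterogeneity step.

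**The concern.** Not finding heterogeneity is different from finding that devices agree. The sample size serves the LLH effect inside one device. A difference in that effect between two devices has roughly twice the variance, so the same patients give a much less sensitive test.

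The pool could combine outpatients on HM2 and HM3 with cardiogenic-shock inpatients on VA ECMO or Impella. A similar LLH effect across those settings cannot be presumed. If the effect differs in part, the gate will often let the devices through, and a single association will be reported across device type mainly because the test had little power. The mediator comparisons in the pooled sample would follow the same decision.

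This holds even if the heterogeneity test is carried out properly. LLH and no-LLH patients are different people, so the matching test is the LLH-by-device interaction in a two-factor model. That test is assumed throughout.

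**Working it through.** **1. The plan's own figure.** Inputs: 20±5 against 26±4 AU, 15 per group, two-sided 0.05. With SD 5 the effect is 6/5 = 1.2 SD. The standard error is √(2/15) = 0.365 SD, and 1.2/0.365 − 1.96 = 1.33, so power is 90.8% (normal) or 88.7% (t). With the pooled SD √((25+16)/2) = 4.53 AU, the effect is 1.33 SD and power is 95.2% or 93.8%. The stated 90% is reproduced, for one device at a time.

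**2. Precision per device.** In SD units, the variance of the LLH difference is v = 1/n(LLH) + 1/n(no LLH), with weight w = 1/v.

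| Device | LLH / no LLH | v | w |
|---|---|---|---|
| HM2 | 15/35 | 0.0952 | 10.5 |
| HM3 | 15/60 | 0.0833 | 12.0 |
| VA ECMO | 15/30 | 0.1000 | 10.0 |
| Impella | 15/30 | 0.1000 | 10.0 |

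The weights sum to 42.5. N = 215, leaving 215 − 8 = 207 residual df.

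**3. Power of the interaction test.** The noncentrality is λ = Σ w(d − d̄)². When one set of devices (total weight A) differs from the rest (total weight B) by δ, this reduces to λ = δ²·AB/(A+B):

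- one acute device against three: 10 × 32.5/42.5 = 7.647, so λ = 7.647δ²;
- both acute against both durable: 20 × 22.5/42.5 = 10.588, so λ = 10.588δ².

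The miss rate is the probability that a noncentral F(3, 207, λ) falls below the critical value: 2.648 at 0.05 and 1.561 at 0.20. Both levels are assumptions, because the plan gives none.

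| True pattern | δ (SD) | λ | Miss at 0.05 | Miss at 0.20 |
|---|---|---|---|---|
| Planned 1.2 SD, lost in one acute device | 1.2 | 11.01 | 20% | 6% |
| Planned 1.2 SD, lost in both acute devices | 1.2 | 15.25 | 8% | 2% |
| Planned 1.2 SD, halved in one acute device | 0.6 | 2.75 | 75% | 48% |
| Planned 1.2 SD, halved in both acute devices | 0.6 | 3.81 | 66% | 38% |
| Assumed 0.5 SD, one acute device differs | 0.5 | 1.91 | 82% | 57% |
| Assumed 0.5 SD, durable against acute | 0.5 | 2.65 | 76% | 49% |

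If HM2 or HM3 is the device that differs by 0.5 SD, the miss rate at 0.05 is 81% or 80%. Simulation with equal SDs agrees. If the SDs are 5 and 4 AU as in the plan, a pooled-variance F test has 12-18% power for a 0.5-SD difference, so the miss rate is 82-88%.

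**4. Post-hoc pairs.** The standard error of a two-device contrast is √(v₁+v₂), from 0.423 (HM2 and HM3) to 0.447 (the two acute devices). The 95% half-width is 1.96 times that, 0.83-0.88 SD, or about 4.2-4.4 AU at SD 5. The planned effect is 6 AU. Power for a 0.5-SD pairwise difference is 20-22%. A pairwise difference must reach about 1.2 SD for 80% power.

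**The case against.** The strongest reply is that the pooled result only supplements the per-device results. The device-specific comparisons are made whatever the heterogeneity test shows, they carry the sample size, and the mediators are compared within each device as well. If LLH has an effect of 0.5 or 0.8 SD in three devices and none in Impella, then among simulated trials that pool and reach significance (about 56-57% of all trials), Impella's own comparison is non-significant about 96% of the time. A reader would see that result beside the pooled one. This stands, and it limits the point to the pooled results.

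Second, 0.5 SD is not a figure from the plan. At that effect size the per-device t tests themselves have only 34-40% power. This also stands, and is why the halving scenarios, built on the plan's own 6 AU, carry more weight here.

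Third, a reader might infer that whenever LLH matters in some pumps and not in others, the usual outcome is to pool. The documents do not support that at the planned effect: complete loss is missed only 20% or 8% of the time at 1.2 SD, and 12% or 4% at 1.33 SD. The gate fails mainly for partial differences and for smaller effects.

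Fourth, the unstated level might be more liberal than 0.05. At 0.20 the 0.5-SD miss rate is still 49-57%.

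**Conclusion.** The concern holds for the pooled PA/A result and the pooled mediator results. The plan makes a non-significant test the sole condition for pooling, and at the planned sizes that test more often than not overlooks a halving of the planned effect: 75% of the time for one acute device and 66% for both.

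These figures assume equal SDs, enrollment as planned, a correct interaction test and a 0.05 gate. The 0.5-SD scenario and the gate level are assumptions, not the plan's.

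Two stronger readings should be resisted. A reader might infer that the plan takes non-significance as proof that LLH acts alike in all four pumps, or that it will credit an effect to a device that has none. The text says neither; it says only which results will be pooled. A reader might also infer that Aim 1's main comparisons are compromised. They are not, because they are made per device and do not pass through the gate.

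This is an inexpensive improvement worth making, and it does not invalidate the aim.

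**What to change.** Replace the pooling sentence with wording such as:

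> A single linear model with device, LLH and LLH-by-device terms will be fitted to all four devices. Device-specific LLH effects and between-device contrasts will be reported with 95% CIs whatever the interaction p value. The device-stratified LLH effect will be reported as an average over the devices studied and read beside the device-specific results. A non-significant interaction will not be described as absence of heterogeneity.

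Use the same device-stratified model for the pooled mediator comparisons, in place of unpaired t tests on the combined sample.

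This changes SAP wording only and needs no new patients, samples or assays. The price is a weaker claim for the pooled result, and between-device intervals that will openly be wide (half-width about 0.83-0.88 SD).

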**Study Population - Inclusion criteria:** Low Level Hemolysis (LLH) is defined as: abnormally elevated LDH  $\geq$  240 U/L, plasma free hemoglobin  $\geq$  10 g/dL, haptoglobin  $\leq$  100 mg/dL. Outpatients  $\geq$  18 years old with ongoing durable CF pump support (HM2 or HM3), off nitrates and sildenafil, will be eligible to participate in this study. If the radial pulse is palpable manually (pulsatile), then those with a systolic blood pressure (BP)  $<$  100 mmHg, taken by a manual blood pressure cuff, will be excluded. If the radial artery pulse is not palpable (non-pulsatile), then those with a Doppler blood pressure  $<$  80 mmHg will be excluded. In non-pulsatile patients, the BP is taken by a Doppler ultrasound at the brachial artery and is closely correlated to the mean arterial BP. Those patients already on sildenafil or nitrates for clinical indications will also be excluded. In addition, patients with an ongoing infection that may predispose to thrombosis will be excluded as will those unwilling or unable to give written, informed consent.

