**Study Protocol:** After obtaining informed consent, baseline demographics and hematologic biomarkers including fasting am PA/A and NO bioavailability measurements (3 tubes [1 tube for platelet aggregometry, 1 tube for exploratory biomarkers including p selectin, CD 40L, GPIIb/IIIa receptor, and 1 tube for NO bioavailability] x 3ml = 9 ml of blood) will be collected. In addition, endothelial function will be assessed by flow mediated dilation of the brachial artery and fingertip temperature changes following a 5 min blood pressure cuff inflation. Patients will be placed, using computerized randomization, into 2 groups to receive the study drug which will be either sildenafil or placebo. More precisely, an enrolled patient will be randomly placed in either the placebo or the sildenafil arm, both of which will be marked as "Study Drug." Neither the patient nor the drug administrator will be aware to which study arm the patient has been designated. Following randomization and if BP is in the acceptable range (see figure 4), 20 mg of the study drug will be administered. Then BP will be recorded every 30 mins for two hours. If BP drop is < 5 mmHg after 2 hours and patient is asymptomatic, they will proceed to take 20 mg of the study drug every 8, starting on day 2 (total 18 doses). Patients will be asked to return to the clinic on day 8 and 20 mg of the study drug will be administered. After 2 hours, which is the time of peak drug concentration, fasting am PA/A and NO bioavailability measurements (3 tubes [1 tube for platelet aggregometry, 1 tube for exploratory biomarkers including p selectin, CD 40L, GPIIb/IIIa receptor, and 1 tube for NO bioavailability] x 3ml = 9 ml of blood) will be collected. In addition, endothelial function will be assessed by flow mediated dilation of the brachial artery and fingertip temperature changes following a 5 min blood pressure cuff inflation. Then the patient will be asked to come back to clinic on the next weekday and if BP is in the acceptable range (see figure 4), 40 mg of the study drug will be administered. If BP remains stable for 2 hours (< 5 mmHg drop and asymptomatic), then patients will continue taking 40 mg every 8 hours. Patients will be asked to return to clinic on day 15. A final 40 mg dose of the study drug will be given and after 2 hours fasting am PA/A and NO bioavailability measurements (3 tubes [1 tube for platelet aggregometry, 1 tube for exploratory biomarkers including p selectin, CD 40L, GPIIb/IIIa receptor, and 1 tube for NO bioavailability] x 3ml = 9 ml of blood) will be collected. In addition, endothelial function will be assessed by flow mediated dilation of the brachial artery and fingertip temperature changes following a 5 min blood pressure cuff inflation. All patients will be on a standard antithrombotic regimen of aspirin 81 mg daily with a target INR of 2-2.5 IU.

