**Statistical analysis, sample size calculations:** The primary measure of PA/A is the change in ADP-induced AUC assessed by platelet aggregometry, which will be compared between the treatment and placebo groups by an independent samples Student's t test. The null hypothesis is that the mean change in PA/A will be the same in both groups at the 15 day time-point. In a prior single-arm study in patients with ongoing hemolysis from SCA, sildenafil reduced PA/A by around 40% from  $30.6\%\pm15.2$  to  $17.3\%\pm12.4$  [17]. If this is the true population effect with standard deviation of the sildenafil induced change in PA/A among patients on durable CF pump support and if there is no expected change in the placebo group, we would need 23 patients per group (46 total patients) to achieve **85% power** to detect a significant difference in mean reduction with a two-sided alpha of 0.05. Analysis will be by intention-to-treat. Although the primary analysis will be unadjusted, secondary analyses will apply linear regression models to adjust for age, sex, race/ethnicity, duration of device implant, type of device (HM2 or 3) and adherence. Given the small sample, adjustment will be limited to no more than 2 additional variables at a time. If device differences are observed, sub-group analyses by device will be performed. For secondary outcomes, the above analyses will be repeated at 8 days and also comparisons of changes in p-selectin, activated GP IIb/IIIa receptor and platelet cGMP at 8 and 15 days.

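### Aim 2 randomises before the first-dose blood pressure check, so a patient can be randomised, never dosed and still fall under intention-to-treat; the cost is probably small and cheap to avoid.

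*Combined protocol and SAP*

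**What the plan says.** The Aim 2 Study Protocol runs in this order: consent, baseline blood and endothelial tests, computerised randomisation, BP check, first dose. On allocation it says "an enrolled patient will be randomly placed in either the placebo or the sildenafil arm", and on the next step "Following randomization and if BP is in the acceptable range (see figure 4), 20 mg of the study drug will be administered". The acceptable range is in figure 4, which is not available here.

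BP is also looked at earlier. The Aim 2 inclusion criteria exclude low BP, by cuff in pulsatile patients (systolic below 100 mmHg) and by Doppler in non-pulsatile patients (below 80 mmHg). The interval between that reading and the first dose is not stated.

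The Aim 2 statistical section says "Analysis will be by intention-to-treat". The change in ADP-induced AUC at day 15 is "compared between the treatment and placebo groups by an independent samples Student's t test". That section plans 23 per group for 85% power. The recruitment plan enrols 62 and allows 25% drop-out, leaving 46 who complete.

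No section says whether a patient who is out of range at the first-dose check is rechecked, deferred or withdrawn, or whether that patient is measured at day 15.

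**The concern.** A patient stopped at this check has been allocated to an arm but has had no drug. Under intention-to-treat the patient stays in that arm. If measured at day 15, a patient assigned to sildenafil contributes no drug effect, which pulls the estimated difference towards zero. If not measured, the patient is a missing outcome that could have been avoided, and the analysis is no longer a full intention-to-treat analysis.

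The check uses nothing that randomisation produces. A BP reading at the same visit, taken just before allocation, would identify nearly all of these patients while they can still be left unrandomised. In a trial this small, each allocated patient who cannot contribute information about the drug matters.

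**Working it through.** **Inputs.** From the Aim 2 statistical section: mean 30.6 before and 17.3 after sildenafil, no change on placebo, 23 per group, two-sided alpha 0.05, power 85%. From the recruitment plan: 62 enrolled, 25% drop-out, 46 completers. Not given, so assumed: the SD of the change, and the share f of patients randomised but never dosed.

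**Step 1: reproduce the stated size.** Difference = 30.6 − 17.3 = 13.3. With the baseline SD of 15.2 used as the SD of change, the normal approximation gives 24 per arm for 85% power, and power 0.843 at 23 per arm. This agrees closely with the plan. The SD that gives exactly 85% at 23 per arm with the t test is 14.72, which is used below. Drop-out: 62 × 0.75 = 46.5, which matches 46 completers.

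**Step 2: undosed patients have no day-15 value.** They are then losses after enrolment. The allowance is 62 × 0.25 = 15.5 patients. With f = 5% the undosed number about 3 (62 × 0.05 = 3.1), and with f = 10% about 6 (62 × 0.10 = 6.2). Both fit within the allowance, so the 46 completers and their 85% power stand. The allowance is not broken down by cause; if other losses alone reached 25%, f = 5% would leave 62 × 0.95 × 0.75 = 44 completers.

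**Step 3: all 62 are measured, 31 per arm.** Assume that undosed patients show no effect and everyone else shows the planned effect.

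- Expected difference = 13.3 × (1 − f)
- Variance in the sildenafil arm = 14.72² + f(1 − f) × 13.3²
- SE = √[(sildenafil variance + 14.72²) / 31]
- Power ≈ Φ(difference / SE − 1.96)

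For f = 10%: difference = 11.97; sildenafil variance = 216.7 + 0.09 × 176.9 = 232.6; SE = √(449.3 / 31) = 3.81; power ≈ Φ(3.14 − 1.96) = Φ(1.18) = 0.88. The simulated t test is about one point lower.

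| Undosed f (assumed) | Expected difference | Power, 31 per arm (t test) |
|---|---|---|
| 0% | 13.30 | about 94% |
| 5% | 12.64 | about 91% |
| 10% | 11.97 | about 87% |
| 15% | 11.31 | about 83% |

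Power passes below 85% somewhere above f = 10%. The attenuation of the estimate is f itself: 5%, 10% or 15% of the true effect.

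**The case against.** The strongest reply is that BP has already been screened. Only a patient whose BP moves out of range between eligibility and first dose, or who meets a different limit in figure 4, is affected, and the text does not rule out a recheck on another day. This stands, and it is why the affected share is probably small. It does not close the gap, because the documents state neither the interval nor that the two sets of limits agree, and the protocol keeps a second check that some patients could fail.

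A reader might infer that power falls from 85% to about 80%, 75% and 70% at 5%, 10% and 15% undosed. That arithmetic is right for undosed patients counted among 23 per arm, but the plan's 23 per arm are completers after drop-out. A patient who never started drug is either not among them or belongs to the larger set of 62.

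A reader might also infer that the p<0.2 interim rule becomes harder to pass. The Addendum describes the 20 patients as having completed the study, so on a plain reading never-dosed patients are not among them.

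Third, a BP reading immediately before dosing serves safety. That stands: the objection is to where randomisation sits, and the existing check should not be removed.

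Finally, later checks matter too: the BP and symptom rule after the first dose, and the one introduced by "Then the patient will be asked to come back to clinic on the next weekday and if BP is in the acceptable range". The rule after the first dose can depend on the arm, and reordering the first check does not address either of them. They are separate points.

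**Conclusion.** The point holds in limited form. The written order allows randomised-but-undosed patients under an intention-to-treat analysis with no stated handling, and this is avoidable. The cost is attenuation and lost precision, or missing data. Bias between arms might be inferred but is not supported: the check precedes any drug in a trial that blinds the patient and the drug administrator, so failure should not differ by arm.

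The size depends on a failure rate that the documents do not give. With no day-15 values, the undosed fit within the 25% drop-out allowance at the rates considered. With all 62 measured, power stays at or above the stated 85% up to roughly 10% undosed. Both results rest on the plan's difference of 13.3 and the back-solved SD of 14.7; the second also assumes that every dosed patient shows the full effect. No effect on the interim analysis is shown.

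**What to change.** For any further enrolment, add a BP reading at the same visit just before randomisation, judged against the existing acceptable range, and randomise only patients who are in range. Keep the existing check before the first dose, and its range, unchanged. This adds a reading and changes no clinical limit.

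Keep intention-to-treat as the primary analysis. State whether randomised-but-undosed patients are followed to day 15, and show results without them as a sensitivity analysis. Making their exclusion the primary analysis is not advised, since it would replace the stated population while the trial is under way.

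Cost: one added step in the Aim 2 Study Protocol and a sentence or two in its statistical section. A few screened patients will not be randomised, and one BP reading may be repeated. No extra visit is needed.

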
Endothelial Function Testing will be conducted by non-invasive methodology. As has been previously well described [32], a vascular ultrasound probe will be used to assess the diameter of the brachial artery at the level of the antecubital fossa in the longitudinal view. Then an arm blood pressure cuff will be inflated beyond the systolic pressure for 5 minutes to cause transient ischemia. After deflation of the arm blood pressure cuff, the brachial artery diameter will be recorded again by the ultrasound vascular probe. In addition, by using the noninvasive Endothelix device, we will simultaneously also record figure tip temperature change before and after cuff deflation, as another measure of endothelial function.

Addendum to study protocol:

Aim 2 of this protocol is a randomized, blinded, placebo-controlled study to assess the effect of sildenafil on platelet function in patients supported by left ventricular assist devices. We originally proposed to enroll 46 patients into this study. At this point, 20 participants have successfully completed the study since enrollment which was initiated in 2019. Due to slower than expected enrollment for a variety of reasons, including the COVID-19 pandemic, a competing trial and a reduction in institutional implantation volume of these devices, it is no longer feasible to reach the originally proposed sample size within the planned study period

ending December 30, 2023.

In discussion with my mentoring team, we propose to amend the study protocol to perform an interim analysis at the current sample size of 20 participants. The statistical plan will be carried out as originally proposed in the study plan. If there is a trend at a  $p<0.2$  for a change in platelet function between groups, then we will readjust the required sample size accordingly for the duration of the enrollment period. If this trend is not apparent, then it would be futile to enroll additional patients into this study aim and further enrollment will stop. In this scenario, we will proceed with analysis of proposed study measures with subsequent reporting of findings.

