**Plan for recruitment, retention, timeline and check points:** Patients on CF MCS are tracked closely in a centralized electronic medical registry kept by the HF group, which we will continue to leverage as a resource to identify patients. Currently, 52 outpatients identified through our CF MCS patient registry on durable devices with LLH are available for screening and at the current implant rate of 5 durable devices per month, 1 additional patient with LLH becomes available every month. With an estimated 35% ineligibility or withholding consent, 95 patients with LLH will need to be screened to enroll 62 patients. With an additional 25% drop-out rate after enrollment, this will leave 46 patients (23 per group) who will complete the study protocol. Since 52 outpatients with CF pumps and LLH are currently available (which is steady state for our program based on prior 3 years) and taking into account 35% ineligibility or unwillingness to participate at screening, we estimate that 34 patients can be immediately enrolled to get a head start. At the current availability of 1 new LLH patients per month, it will take an additional 42 months to screen and enroll the remaining patients. We will conduct checkpoints every 6 months examining if the anticipated enrollment (table 2) is being achieved. If enrollment is not met by 2 consecutive check points, we may increase recruitment an additional 6-12 months.

**Anticipated results and experimental problems:** We expect that enhancement of NO signaling with Sildenafil in patients with low level hemolysis will lead to a reduction in PA/A. If changes in PA/A are not observed, then exogenous PA/A will be assessed with platelet poor plasma. If PA/A is not affected, then follow-up experiments will have to be designed to identify the LDH and plasma free hemoglobin threshold value at which lower-level hemolysis increases PA/A.

Alternatively, if the expected reduction in PA/A is not observed with sildenafil we may try other pharmacological agents that also enhance NO signaling such as nitrates.

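### Aim 2 addendum: p≥0.2 at 20 completers is treated as futility, though a trial with the full planned effect meets it about 24% of the time, and the stated 85% power is not that of the amended design

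*Combined protocol and SAP*

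**What the plan says.** The Aim 2 addendum reports that "20 participants have successfully completed the study since enrollment which was initiated in 2019" and that, for several reasons, "it is no longer feasible to reach the originally proposed sample size within the planned study period", which ends on December 30, 2023. It then adds an interim comparison at these 20 participants with two branches:

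- Below p=0.2, recruitment goes on. The wording of this branch, which refers to a trend, is: "for a change in platelet function between groups, then we will readjust the required sample size accordingly for the duration of the enrollment period".
- At p=0.2 or above, the other branch applies, and here the addendum reads: "If this trend is not apparent, then it would be futile to enroll additional patients into this study aim and further enrollment will stop". The study measures are then analysed and the findings reported.

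On the analysis it says: "The statistical plan will be carried out as originally proposed in the study plan". It gives no attainable total, revised power, direction for the trend or method of re-sizing.

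The Aim 2 statistical section plans a two-sided Student's t test on change at day 15 with alpha 0.05, and says "we would need 23 patients per group (46 total patients) to achieve" its target, which it puts at 85% power. The recruitment section adds: "If enrollment is not met by 2 consecutive check points, we may increase recruitment an additional 6-12 months". The Aim 2 section on anticipated results says that "if the expected reduction in PA/A is not observed with sildenafil we may try other pharmacological agents".

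**The concern.** Whether more patients are worth enrolling depends on how many can still be reached and on which effects the data have ruled out. The gate uses neither. A p-value of 0.2 or more in 20 patients can occur with no effect or with the whole planned effect, so it does not show futility by itself.

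Two things are at stake. First, a result that fits the planned effect may be taken as a failed test of sildenafil, since the plan attaches next steps to a reduction that is not observed. Second, the only power figure in the document belongs to a 46-patient design with no interim stop. The addendum gives up that sample size and puts no other figure in its place.

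**Working it through.** **Inputs.** From the Aim 2 statistical section: 30.6 (SD 15.2) before and 17.3 (SD 12.4) after sildenafil, so the effect is 30.6 - 17.3 = 13.3; no change on placebo; two-sided alpha 0.05; 23 per arm; 85% power. From the addendum: 20 completers and p<0.2. Assumed: 10 per arm (allocation is 1:1) and a two-sided interim p. A positive estimate means a larger reduction on sildenafil.

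**The plan's own figure.** No SD of the change is stated. With SD 15.2, power at 23 per arm is 82.7% by t test (84.3% by normal approximation), which is close to 85%. Solving the t-test power for exactly 85% at 23 per arm gives d = 0.9035, so SD = 13.3/0.9035 = 14.7. This is used below.

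**Power at 20.** Non-central t with 2n - 2 degrees of freedom and non-centrality d√(n/2). At n = 10 per arm this is 0.9035 × √5 = 2.02 on 18 df.

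- Power at alpha 0.05: 48.1% (45.7% at SD 15.2, 52.8% at SD 13.9).
- Chance of p≥0.2 with the planned effect: 24.4% (26.4% at SD 15.2, 20.8% at SD 13.9).
- Outer range: 14% at SD 12.4 and 42% at SD 19.6 = √(15.2² + 12.4²), the value for zero correlation. These extremes give 94% and 61% power at 23 per arm, so they do not reproduce the plan's 85%.

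**What p≥0.2 rules out, at SD 14.7.** SE = 14.72 × √(2/10) = 6.58.

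- Favourable boundary estimate: 1.330 × 6.58 = 8.8.
- 95% CI half-width: 2.101 × 6.58 = 13.8, so the CI is -5.1 to 22.6 and contains both 0 and 13.3.
- The upper limit falls below 13.3 only when the estimate is below 13.3 - 13.8 = about -0.5.
- By simulation, the CI excludes 13.3 in about 48% of stopped trials with no effect and about 10% of stopped trials with the planned effect.

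**Cost in power, planned effect true (simulation).**

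| Total reached | Power, no rule | Power, p<0.2 rule | Points lost | Stopped trials that would have become significant |
|---|---|---|---|---|
| 22 | 52.3% | 52.3% | 0 | 0% |
| 24 | 56.2% | 55.8% | 0.4 | 1.6% |
| 26 | 59.9% | 58.4% | 1.5 | 6% |
| 30 | 66.6% | 62.2% | 4.4 | 18% |
| 46 | 85.0% | 70.4% | 14.6 | 60% |

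**Reachable total, illustration only.** A start within 2019 gives T = 48 to 60 months to December 30, 2023. With m months left at the observed pace, further completers = 20m/(T - m). For m = 6 this is 120/54 to 120/42 = 2.2 to 2.9; for m = 12, 240/48 to 240/36 = 5.0 to 6.7. The total would be about 22 to 27. The months left are an assumption.

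**Type I error.** Using p<0.2 only as a gate does not inflate it (3% to 5% when only the final test counts). If p<0.05 also counted as success at the interim, it is about 6% to 7%.

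**The case against.** The best defence is that the addendum speaks of the futility of enrolling more patients, directly after saying that 46 is out of reach. On that reading it makes a practical statement, and the table supports it: at totals of 22 to 26, at most 6% of stopped trials with the planned effect would have become significant. That stands, and it is a reason to call the stop feasibility-driven. It does not stand as a reading of the p-value, because the gate makes the word depend on p and not on the reachable number.

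It is also fair that the 85% is worded conditionally on 23 per group, and that keeping the statistical plan most naturally refers to the analysis. But no other power is given, and with this rule even 46 patients would give only about 70%.

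Four stronger readings are tempting and are not supported:

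- *Every stopped result is inconclusive.* About 48% of stopped trials with no effect have a CI that excludes 13.3, which is evidence against the planned effect.
- *The rule throws away much power.* The 14.6-point loss needs 46 patients, which the addendum rules out by December 30, 2023. Whether the 6-12 month extension is still available or already inside that date is not settled.
- *The trial will be reported as showing no effect.* The addendum commits to reporting the findings and does not say this. The next steps are worded as possibilities and are not tied to the interim rule. The risk is that nothing guards against that reading.
- *The missing direction is a serious flaw.* A wrong-direction trend continues enrolment in about 10% of trials with no effect and under 0.1% with the planned effect, and does not inflate type I error. It is minor.

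**Conclusion.** The point holds in a limited form and should be fixed. Meeting p≥0.2 at 20 completers does not by itself establish futility: roughly one trial in four with the full planned effect would be stopped, and results near the favourable boundary fit both no effect and that effect. Nor does the 85% describe the amended design, which has about 48% power if it ends at 20. At the totals that look likely, little power is lost, so the harm lies in how a stop is labelled and interpreted and in the power a reader would take from the document.

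This rests on 10 completers per arm, a two-sided interim p-value and an SD of change inferred from the plan's own power statement. For SDs of 13.9 to 15.2, power at 20 is 53% to 46%.

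**What to change.** 1. **Reachable total and power.** In the addendum, state the total attainable by the end of enrolment, and whether the 6-12 month extension is counted in it. Replace the 85% with the power at that total: 48% at 20, 52% at 22, 56% at 24, 60% at 26 or 67% at 30. If the p<0.2 gate is kept, use the lower column of the table.
2. **Label and inference.** Describe a stop at 20 as feasibility-driven, not as futility or evidence of no effect. Report the estimate with its 95% CI and judge it against both 0 and 13.3: inconclusive if the CI includes both, evidence against the planned effect if it excludes 13.3. Tie the next steps for an unobserved reduction to that reading.
3. **If enrolment continues.** Fix the final number from feasibility, up to 46. Do not re-size from the observed interim effect, and make no efficacy claim at the interim.

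Replacing p<0.2 with a conditional-power rule is optional. With a 10% cutoff it gains 0 points at 22, 0.3 at 24 and 1.3 at 26, and at 22 it stops more trials with the planned effect (30% against 24%).

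The cost is some rewording, one restated figure and a less favourable stated power. No extra patients are required.
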